3.2. Endpoints

The gathering of information on the therapeutic effects of the treatment with the **HEDUSSIN®** medicinal product includes the assessment of: the number of days until full recovery of the Patient measured from the day of the 1st visit until the closure of the observation – the day of the 2nd visit.

- Exclusion from the Study the number of days measured from the day of the 1st visit until the occurrence of complications, intensification of the state, occurrence of additional infections, etc.

 visit 2: closure of the observation and the conducting of a medical interview on the health status/Patient wellbeing.
- The change in the intensity of the symptoms, associated with the respiratory system, resulting
 from the treatment will be assessed on the basis of the BSS scale (Bronchitis Severity Scale)
 (evaluation of the measurements taken during visit 1 and 2)
- The evaluation of the changes in the overall wellbeing resulting from the treatment will be based on the VAS scale (Visual Analog Scale) (evaluation of the measurements taken during visit 1 and 2)
- The evaluation of the treatment tolerance based on the occurrence of sleep quality disturbances and weakness feeling will take place on the basis of a 5-level estimation scale (evaluation of the measurements taken during visit 1 and 2)

All adverse effects caused by the drug must be reported to **Phytopharm Klęka S.A.** or the URPL or to the Study Organizer via the **www.dzialanianiepozadane.com** website.

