5.4. Procedures for treatment discontinuation or if the patient withdraws from the study

If the patient is excluded from the Study (i.e. they discontinue the participation in the Study before the evaluations schedule in the Assessment Protocol), the main reason for discontinuation will be recorded in the Study Questionnaire (SQ). Discontinuation from the study due to adverse effects must be adequately described in the patient records.

The investigator provides patients excluded from the study with adequate further treatment - personally or by another doctor with the existing documentation of the disease course.

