6. METHODOLOGY

6.1. Schedule of the Study

A summary of observations and assessments that will be conducted during the study is presented in the following table.

Table1. Schedule of the assessments during the Study realisation

PROTOCOL FOR A NON-

INTERVENTIONAL

STUDY

Procedures for particular assessments	Visit 1*	Visit 2*
Demographic data	Х	
Qualification of the Patient into the PAES Study (inclusion criteria)	Х	
History concerning comorbidities and their treatments	Х	Х
Basic diagnosis and its duration	Х	
The dose of the medicinal product used		Х
The assessment of :		
 The symptoms associated with the respiratory system (BSS scale) 		
Assessment of the body temperature	Χ	Х
Assessment of the overall wellbeing (VAS scale)		
Assessment of the sleep quality disturbances		
The use of concomitant treatment		
Duration of the infection (number of days)		Х
Reporting adverse effects related to the HEDUSSIN ® medicinal product use		Х

^{*}The assessments will take place as part of the routine Patient observation

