6.2. Assessments in a specialist and primary care clinics under the study

6.2.1. Initial visit (Visit 1) - (day 0)

The Study Questionnaire of Patients using the **HEDUSSIN®** medicinal product, in accordance with the leading physician as well as in accordance with the marketing authorization criteria, shall contain the following information:

- patient number;
- patient initials;
- demographic data;
- interview data on comorbidities;
- initial diagnosis;
- data on the long-term medicine administration in the treatment of comorbidities;
- decision on the Patient's compliance with the inclusion criteria and noncompliance with the exclusion criteria;
- data on the recommended dose of the HEDUSSIN® medicinal product;
- the assessment of the following symptoms:
 - 1. cough severity (from 0 to 4)
 - 2. dyspnoea (from 0 to 4)
 - 3. auscultatory changes during the cough (from 0 to 4)
 - 4. chest pain during the cough (from 0 to 4)
 - 5. hoarse breathing (from 0 to 4)
 - *in accordance with the 5-level BSS scale (Bronchitis Severity Scale) where:
 - 0- absent; 1- mild; 2- moderate; 3- severe; 4- very severe

Study number: EUP/HED/008/2016

VERSION DATE: 21.11.2016

- assessment of the body temperature;
- evaluation of the weakness feeling* *on a 5-level estimation scale where: 0- absent; 1- mild; 2- moderate; 3- severe; 4- very severe
- assessment of the overall wellbeing using the VAS scale;
- assessment of the sleep quality disturbances;
- the used concomitant treatment.
- 6.2.2. Visit 2 (approximately 7-10 days after the previous visit) in accordance to the schedule resulting from the clinical needs of the Patient

The Patients will be present on the control visits in the study centre at the scheduled time. During these visits, the Investigator will collect and record in the Study Questionnaire (SQ) the following information:

Duration of the infection (number of days until the symptoms receded)

A secondary conducting of:

- The assessment of the symptoms associated with the respiratory system on the basis of the BSS scale
- The evaluation of the body temperature
- The assessment of the weakness feeling on the basis of a 5-level estimation scale
- The assessment of the wellbeing based on the VAS scale
- The assessment of the sleep quality disturbances
- The used concomitant treatment

The Patient Observation last approximately 10 days.

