10.4.2. Distribution of patients and cases of exclusion from the study

The number of patients treated, the number of patients who discontinued treatment with the study drug, and the number of patients who participated in the study visits will be presented in the form of tables. The main reasons for patients' discontinuation from participation in the study will be presented in the form of tables.

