12.2. The scope of the data collected

The Investigator is required to record all the data relating to the procedures detailed in the Study Protocol, including use of the study drug in the Study Questionnaires provided for the purpose of this study.

The Investigator is required to sign the page of the SQ relating to the completion of study and a certificate of study completion to prove that all entered data is accurate and complete.

Any corrections in the SQ and source documents must be placed in such a way that the original entries were still legible (strikethrough single thin line). If the reason for the change is not obvious, this should be clearly stated.

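### Section 3.2 sets an endpoint of days from Visit 1 to complications, worsening or additional infection, but no listed item records the day of that event

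*Protocol*

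**What the plan says.** Among the endpoints in section 3.2 of the protocol, under exclusion from the study, is "the number of days measured from the day of the 1st visit until the occurrence of complications, intensification of the state" or an additional infection. The same part of 3.2 describes Visit 2 as "closure of the observation and the conducting of a medical interview on the health status/Patient wellbeing".

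The collection lists are as follows.

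- **Section 6.1, Table 1.** The only day count on the course of the illness after Visit 1 is "Duration of the infection (number of days", at Visit 2. A row that could touch on a new condition is "History concerning comorbidities and their treatments", at both visits.
- **Section 6.2.2, Visit 2.** The day count is spelled out as "Duration of the infection (number of days until the symptoms receded". The rest repeats the Visit 1 assessments: BSS, temperature, weakness, VAS, sleep and concomitant treatment.
- **Section 5.4.** When a child leaves before the scheduled evaluations, "the main reason for discontinuation will be recorded in the Study Questionnaire (SQ".
- **Section 10.4.2.** The main reasons for patients' "discontinuation from participation in the study will be presented in the form of tables".

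Section 10.2 confines the efficacy analysis to patients who took part in all assessments. Section 10.1 defines a treated patient as one who received at least one dose.

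**The concern.** The endpoint is a number of days, so it needs an event and the day it happened. The protocol's own lists ask for neither at Visit 2, and on early exit they ask only for the reason. A site could complete every listed item and still provide nothing from which this endpoint can be calculated. An analysis plan written later cannot recover a date that was not collected.

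This is the only endpoint in the section 3.2 list defined by failure on treatment. If it has no data, and the children it describes are also outside the efficacy population, the efficacy results rest on days to recovery and symptom change in children who stayed to the end. Sections 1.3 and 3.3 say that the results will be used for marketing campaigns and for training doctors, so the direction of that tilt matters.

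**Working it through.** There is no plan figure to reproduce. The check sets what the endpoint needs against what is listed.

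**1. What the endpoint needs.** Days to event = date of event − date of Visit 1. Visit 1 is day 0 (section 6.2.1), so the missing quantity is the date of the event.

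**2. Where that date could come from.**

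| Source | Event itself | Day of event |
|---|---|---|
| Table 1 (6.1) | No row for complication, worsening or additional infection; comorbidity history at Visit 2 might catch a new condition | Not listed |
| Visit 2 list (6.2.2) | No item | Not listed; the only day count runs to resolution of symptoms |
| Discontinuation record (5.4) | Yes, as the main reason, if it led to exclusion | Not listed, nor is the day of exclusion |
| Tabulation of exits (10.4.2) | Counts by main reason | No time to exit |

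**3. Whether the existing day count can stand in.** It cannot. It measures the time until symptoms went away. For a child who got worse it is either undefined or a different, later day.

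**4. Whether the visit date can stand in.** Visit 2 falls about 7 to 10 days after Visit 1. For a child seen at Visit 2, knowing only that the event came before the visit places it anywhere between day 0 and day 7 to 10. That is the whole range the endpoint can take, so it carries almost no timing information. For a child who left earlier, not even that upper limit is a listed item.

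**5. Who is left in the efficacy results.** Exclusion under 5.4 means leaving before the scheduled evaluations. The efficacy set in 10.2 requires all assessments. A child excluded for worsening before Visit 2 therefore meets 5.4 and fails 10.2. The omission depends on outcome: it removes poor courses and not good ones.

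**6. Scale.** The protocol gives no rate for these events. As an illustration only, with an assumed rate of 3% to 10%:

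- 500 × 0.03 = 15 children
- 500 × 0.10 = 50 children

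These are the children for whom no listed item would hold the day of the event. The figures are arithmetic on an assumption and not an estimate.

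**The case against.** Four arguments stand against the point.

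- **The event is recorded.** A reader might infer that failures go unrecorded altogether. The documents do not support that. Section 3.2 frames the endpoint as exclusion, section 5.4 puts the main reason in the questionnaire, and 10.4.2 tabulates it. For excluded children the type of event is available. This stands, and it confines the gap to the day of the event and to events in children who are not excluded.
- **The questionnaire is not shown.** A reader might infer that the endpoint cannot be produced at all. That goes too far. The form may hold a date field, section 3.2 provides an interview at Visit 2, and section 12.2 says: "The Investigator is required to record all the data relating to the procedures detailed in the Study Protocol". But the interview is described only in terms of health status and wellbeing, and the procedures that 12.2 refers to do not include this date. The completeness checks in sections 11 and 12.4 are made on the questionnaire and on compliance with the protocol, so nothing in the protocol text would lead to a query about it.
- **Worsening shows elsewhere.** A reader might infer that nothing else could reveal failure. In fact BSS, VAS and temperature at both visits can show that a child is worse, and section 2.1 lists the start of an antibiotic among the bases for judging efficacy. This stands for children seen at Visit 2. It does not help with children who left before it.
- **The wording of 3.2 is unclear.** The text on Visit 2 may be a separate list entry and not the collection point for this endpoint. Visit 2 is also timed by clinical need, so a return for worsening could itself serve as the closing visit. Both readings are possible. Neither supplies a date item, and no text says that such a return is to be treated as Visit 2.

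**Conclusion.** The point holds in this form: the protocol names a time-to-failure endpoint, and none of its collection lists includes the day of failure. No Visit 2 item asks about the event itself. Failures that lead to exclusion can be counted by reason; the time to failure is not supported by any listed item. With efficacy restricted to patients who took part in all assessments, children excluded for worsening are also missing from the efficacy results, which makes those results lean towards recovery.

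The size of the lean cannot be computed from the protocol; the 15 to 50 children rest entirely on the assumed 3% to 10%. The conclusion assumes that the questionnaire follows the lists in 5.4, 6.1 and 6.2.2. If the form already carries the date, what remains is to bring the protocol lists into line with it and to settle the population for this endpoint. The gap should be closed: it is an inconsistency within the protocol and concerns data that later analysis cannot supply.

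**What to change.** 1. Add one item to Table 1, to the Visit 2 list in 6.2.2 and to the discontinuation record in 5.4: *complication / worsening / additional infection: yes or no, type, date*.
2. State in 5.4 that where a child is seen for such an event, the Visit 2 assessments (BSS, VAS, temperature, concomitant treatment) are completed at that contact as the closing assessment.
3. State in section 10 that the number, type and day of these events are reported among all treated patients as defined in 10.1, not only those with all assessments, next to days to recovery.
4. Count separately the children with no further contact. Section 5.4 allows care to pass to another doctor and section 10.5 foresees children whose fate is unknown, so some will still lack a date and should be shown as such.

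The cost is one more questionnaire item and a few sentences of protocol text. No visit or diagnostic procedure is added, so the non-interventional character is unchanged. The reported results may be somewhat less favourable.

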1.2. Information on the study drug

HEDUSSIN® (active substance: dry ivy leave extract).

HEDUSSIN[®] is recommended for use in treatment of wet cough of various aetiology as an agent facilitating expectoration – expectorant – in both adults and children. The medicine is administered orally and should be shaken before use.

In children aged 2-5, it is recommended to administer 2 ml of the syrup twice daily (which corresponds to 33 mg of dry ivy leave extract daily).

In children aged 6-12, it is recommended to administer 4 ml of the syrup twice daily (which corresponds to 66 mg of dry ivy leave extract daily).

In adults and children above the age of 12, it is recommended to administer 6 ml of the syrup twice daily (which corresponds to 99 mg of dry ivy leave extract daily).

Contraindications for the use of the dry extract of ivy leaves include:

- Hypersensitivity to the active substance, other plants from the Araliaceae family or any of the
 excipients (non-crystallizing liquid sorbitol, potassium sorbate, xanthan gum, anhydrous citric
 acid)
- Age below 2 years.

Persistent or recurring cough in children aged 2 to 4 requires a thorough diagnostic before the commencement of the treatment.

In case of the occurrence of dyspnoea, fever or purulent sputum, one should seek advice from a doctor or pharmacist.

It is not recommended to administer the **HEDUSSIN**^R syrup concomitantly with antitussive medicine such as codeine or dextromethorphan. Caution is recommended when administering the syrup in Patients suffering from gastritis or the peptic ulcer disease.

The HEDUSSIN® syrup contains sorbitol, therefore it should not be used by Patients with rare inherited fructose intolerance disorders.

There is no data on the influence of the medicinal product on fertility. The usage safety during pregnancy and breastfeeding has not been established. Therefore, it is not recommended to use the product during that time.

The research on the influence of the preparation on the ability to operate machines has not been conducted.

Interactions with other medicinal products and other forms of interactions

No research conducted.

Study number: EUP/HED/008/2016

VERSION DATE: 21.11.2016

Adverse effects resulting from the use of the HEDUSSIN® medicinal product include:

- Very common (≥ 1/10): none
- Common (≥1/100 to <1/10): nausea, vomiting, diarrhoea
- Uncommon (≥1/1000 to <1/100): allergic reactions (hives, skin rash, angioedema, dyspnoea)

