2.2. The additional aim of the Study

The assessment of the tolerance of the recommended therapy in the course of the infection with wet cough.

The assessment of the tolerance of the **HEDUSSIN®** syrup has been conducted on the basis of:

- 1. Sleep quality disturbances (intermittent sleep, shallow sleep, insomnia)
- 2. The feeling of weakness*

*The evaluation will be conducted on the basis of a 5-level estimation scale where:

0- absent; 1- mild; 2- moderate; 3- severe; 4- very severe

3. The VAS scale focused on the overall wellbeing (from 0 to 10)

^{*}The assessment will be carried out on the basis of the BSS (Bronchitis Severity Score) scale where:

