5.2. Inclusion criteria

Study number: EUP/HED/008/2016

VERSION DATE: 21.11.2016

Each study participant must meet the following criteria:

- Patient of either sex, aged 2 to 12
- Diagnosis of a productive (wet) cough of various aetiology

The inclusion into the Study will take place during the 1st visit. Only Patients in which the earlier recommendation to use HEDUSSIN® in the therapy of productive cough of various aetiology was made due to solely medical reasons and independently from this Study, and who did not take the first dose of the syrup at the moment of the inclusion, are eligible. The inclusion of the patient into the group where the given treatment method is used should not result from the study protocol. It should be dependent solely on the current medical practice and remain in accordance with the current medical knowledge.

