10.2. Analyses, populations, definitions

The analysis of the data on the efficacy will be conducted on the basis of the results of the changes in the intensity of symptoms associated with the respiratory system, the overall wellbeing and the duration of the infection in Patients who participated in all of the assessments outlined in the Study Protocol.

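### The tolerance endpoint follows recovery from the infection, leaves out the product's listed reactions, and is not linked to the adverse effect data already planned

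*Protocol*

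**What the plan says.** **The aim.** Protocol section 2.2 judges tolerance of the syrup on three items: sleep disturbance, weakness on a 0 to 4 scale, and "The VAS scale focused on the overall wellbeing (from 0 to 10". It does not mention adverse effects.

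**The endpoint.** Section 3.2 describes "The evaluation of the treatment tolerance based on the occurrence of sleep quality disturbances and weakness feeling", measured at Visits 1 and 2. The VAS is a separate endpoint there: "The evaluation of the changes in the overall wellbeing resulting from the treatment will be based on the VAS scale". Section 7.1.1 uses wellbeing to assess efficacy, and section 10.2 bases the efficacy analysis on respiratory symptoms, "the overall wellbeing and the duration of the infection".

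**The timing.** Inclusion takes place at Visit 1, and under section 5.2 only children "who did not take the first dose of the syrup at the moment of the inclusion, are eligible". Section 6.2.1 has sleep, weakness and VAS scored at that visit, and 6.2.2 repeats them about 7 to 10 days later. Section 3.1.2 describes an open-label, non-randomised study, and no comparison group is planned.

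**The known reactions.** Section 1.2 lists "Common (≥1/100 to <1/10): nausea, vomiting, diarrhoea", with allergic reactions as uncommon. Sleep disturbance and weakness are not on the list.

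**The adverse effect data.** Table 1 schedules reporting of related adverse effects at Visit 2. Section 9 obliges the investigator to report each related event. Section 10.4.3 plans MedDRA-coded tables of prevalence, maximum intensity, relationship to the drug and discontinuations due to adverse effects, and calls this analysis auxiliary to efficacy.

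**The concern.** A tolerance endpoint should get worse when the drug is poorly tolerated. Sleep disturbance, weakness and poor wellbeing are what a child with a respiratory infection has on the day of the visit, and they can be expected to ease over the next 7 to 10 days with or without the syrup. With no comparison group, the change from Visit 1 to Visit 2 mixes recovery with any harm from the drug, and recovery will usually be the larger part. The reactions known for this product do not enter the definition at all.

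The additional aim could then be reported as met because the children got better. Sections 1.3 and 3.3 say that the data will serve marketing campaigns and professional training, so a fall in weakness and sleep disturbance could be presented there as a tolerability result.

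A statistical analysis plan cannot put this right on its own. The aim and the endpoint are set in the protocol, and a reaction that was not asked about at Visit 2 cannot be recovered at analysis.

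**Working it through.** The protocol gives no figure for tolerance, so there is none to reproduce. The check traces the items through the document and then illustrates the size of the masking.

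**1. Where each item appears**

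| Item | 2.2 | 3.2 | Table 1 | 6.2.1 (Visit 1) | 6.2.2 (Visit 2) | 7.1.1 and 10.2 |
|---|---|---|---|---|---|---|
| Sleep disturbance | tolerance | tolerance | both visits | yes | yes | no |
| Weakness | tolerance | tolerance | not listed | yes | yes | no |
| VAS wellbeing | tolerance | separate endpoint | both visits | yes | yes | efficacy |
| Related adverse effects | no | reporting duty only, not part of tolerance | Visit 2 | no | not listed | no |

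Three things follow. No section links adverse effects to the tolerance aim. Sections 2.2 and 3.2 disagree on whether the VAS measures tolerance. Table 1 and 6.2.2 do not match: Table 1 omits weakness, and 6.2.2 omits adverse effects.

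**2. How far recovery can hide harm (illustration)**

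The protocol gives none of these rates, so all three are assumptions:
- p, the proportion with the symptom at Visit 1: 30% to 80%
- r, the proportion of those whose symptom resolves with the illness: 70% to 90%
- d, the proportion in whom the drug causes the symptom: 0% to 10%, independent of the illness

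Prevalence at Visit 2 = 1 − (1 − p(1 − r))(1 − d).

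- p = 50%, r = 70%, d = 0: 1 − (1 − 0.15) × 1 = 15%.
- p = 50%, r = 70%, d = 10%: 1 − 0.85 × 0.90 = 23.5%.
- Smallest fall in the range (p = 30%, r = 70%, d = 10%): 1 − 0.91 × 0.90 = 18.1%, a change of −11.9 points.
- Largest fall (p = 80%, r = 90%, d = 0): 8%, a change of −72 points.

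Visit 2 is below Visit 1 in every combination. Setting Visit 2 equal to Visit 1 gives the drug effect at which the measure would first show no improvement: d = 1 − (1 − p)/(1 − p(1 − r)). For p = 50%, r = 70% this is 1 − 0.50/0.85 = 41%. At p = 30%, r = 70% it is 1 − 0.70/0.91 = 23%, and at p = 80%, r = 90% it is 1 − 0.20/0.92 = 78%.

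**3. What the adverse effect data could show**

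Take n = 500 as in section 10.3, all treated and with full reporting (section 5.1 also gives 3000, a separate inconsistency). The range that section 1.2 calls common, 1% to 10%, gives 500 × 0.01 = 5 to 500 × 0.10 = 50 expected cases of each gastrointestinal reaction. At 1%, the chance of seeing at least one is 1 − 0.99^500 = 99.3%. For an assumed true rate of 5%, the 95% half-width is 1.96 × √(0.05 × 0.95/500) = 0.019, about 1.9 percentage points. A usable tolerance estimate is therefore within reach from data of a kind the protocol already intends to collect.

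**The case against.** The strongest reply is that the protocol does not rely on these scales alone. Table 1 places related adverse effects at Visit 2, section 9 makes reporting a duty, sections 5.4 and 10.4.2 have reasons for discontinuation recorded and tabulated, and 10.4.3 plans the adverse effect tables. If a tenth of the children had a gastrointestinal reaction and it was reported, about 50 cases would appear there. That stands. A reader might infer that intolerance goes unmeasured or that the additional aim cannot be answered, and the documents do not support either.

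Three further readings also go too far:

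- *The pre-dose baseline is the mistake.* It is not. A pre-dose rating is needed to recognise new or worsened events, and 10.4.3 uses it that way. The fault is a before-and-after comparison of illness symptoms with no control.
- *Improvement in the VAS is counted twice.* No composite or combined success rule is defined. What the text shows is disagreement over the role of the VAS.
- *A gastrointestinal reaction would leave the tolerance items unchanged.* Nothing shows this. A child who vomits may also feel weak. The items are insensitive to such reactions and not specific to them.

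It can also be said that sleep is not purely an illness symptom: section 1.1 says ivy preparations should not be used in the evening, and the overdosage text in 1.2 mentions agitation. The protocol does not connect either to the sleep item, and without a control a drug effect on sleep would still be mixed with recovery. Finally, the questionnaire is not shown and may already contain reaction items, but no section of the protocol requires the listed reactions to be asked about one by one.

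What the reply leaves untouched is the definition. The adverse effect analysis is limited to events judged related, is called auxiliary, is missing from 6.2.2, and is not tied to 2.2 or to the tolerance endpoint in 3.2.

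**Conclusion.** The point holds as a fault of definition. As 2.2 and 3.2 are written, tolerance would be reported from items that improve as the infection clears, and a tolerance problem could be hidden by recovery. Under the assumed rates, the drug would have to cause the symptom in at least 23% of children, and in some combinations 78%, before the measure stopped showing improvement. Those figures rest on assumed prevalence and recovery rates and on independence of drug effect and illness. The direction of the bias needs only that these symptoms tend to ease over 7 to 10 days.

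The conclusion does not extend to safety data being absent. Related adverse effects are planned for collection and tabulation, and with 500 children reactions in the common range would very probably be seen if reported. The defect is that these data do not define tolerance, that the visit descriptions disagree about collecting them, and that the VAS has inconsistent roles across 2.2, 3.2, 7.1.1 and 10.2. The protocol should be changed, because the definition decides what the study can claim about tolerance.

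**What to change.** 1. In 2.2 and 3.2, define tolerance as (a) the proportion of Treated Patients (section 10.1) with at least one adverse reaction and (b) the proportion who discontinued the syrup because of one, each with a 95% CI, drawn from the data planned in 10.4.3. State how many treated children have no Visit 2 information.
2. Ask about nausea, vomiting, diarrhoea and allergic reaction as separate yes/no items at Visit 2, so that the result does not depend on spontaneous reporting.
3. Report sleep disturbance, weakness and VAS wellbeing as illness outcomes only, and take the VAS out of 2.2.
4. Align 2.2, 3.2, 6.2.2 and Table 1: add adverse effects to 6.2.2 and weakness to Table 1.

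The cost is a few more questionnaire items and rewording of these sections, with no extra visit. The sponsor should expect that the tolerance result may look less favourable than an improvement in illness symptoms would.
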